4.1.16. Table 16. All Deaths

		ITT Population	
		N = XX	
		n/N (%)	[95% CI]
All-cause Mortality		XX/XX (XX.X%)	[XX% - XX%]

4.1.17. Table 17. Protocol Deviations according investigator without COVID-19

Type of Deviation	ITT Population		
	Total Number of Events	Number of patients n	n/N (%) [95% CI]
Protocol Deviation Type 1	XX	XX	XX/XX (XX.X%) [XX% - XX%]
Protocol Deviation Description 1	XX	XX	XX/XX (XX.X%) [XX% - XX%]
Protocol Deviation Description n	XX	XX	XX/XX (XX.X%) [XX% - XX%]
Protocol Deviation Type n	XX	XX	XX/XX (XX.X%) [XX% - XX%]
Protocol Deviation Description 1	XX	XX	XX/XX (XX.X%) [XX% - XX%]
Protocol Deviation Description n	XX	XX	XX/XX (XX.X%) [XX% - XX%]

4.1.18. Table 18. Protocol Deviations according investigator with COVID-19

	ITT Population
--	----------------

CONFIDENTIEL / CONFIDENTIAL

Toute reproduction ou distribution, totale ou partielle, de ce document, sans autorisation préalable de ICON PLC est interdite.
Reproduction and distribution of this document, in whole or in part, is strictly forbidden without prior authorization from ICON PLC.

	STATISTICAL ANALYSIS PLAN	FARAPULSE PersAFOne SAP V1.0 PERSAFONE Page 46 /49
---	----------------------------------	--

Type of Deviation	N = XX		
	Total Number of Events	Number of patients n	n/N (%) [95% CI]
Protocol Deviation Type 1	XX	XX	XX/XX (XX.X%) [XX% - XX%]
Protocol Deviation Description 1	XX	XX	XX/XX (XX.X%) [XX% - XX%]
Protocol Deviation Description n	XX	XX	XX/XX (XX.X%) [XX% - XX%]
Protocol Deviation Type n	XX	XX	XX/XX (XX.X%) [XX% - XX%]
Protocol Deviation Description 1	XX	XX	XX/XX (XX.X%) [XX% - XX%]
Protocol Deviation Description n	XX	XX	XX/XX (XX.X%) [XX% - XX%]

4.1.19. Table 19. Device Deficiency Summary Table

	ITT Population N = 25
Device deficiency rate	XX/XX (XX%) [XX% - XX%]

CONFIDENTIEL / CONFIDENTIAL

Toute reproduction ou distribution, totale ou partielle, de ce document, sans autorisation préalable de ICON PLC est interdite.
Reproduction and distribution of this document, in whole or in part, is strictly forbidden without prior authorization from ICON PLC.

	STATISTICAL ANALYSIS PLAN	FARAPULSE PersAFOne SAP V1.0 PERSAFONE Page 47 /49
---	----------------------------------	--

4.2. Listings

- 4.2.1. **Listing 1: Patients populations, reasons of non-inclusion in the different population, withdrawals and follow-up duration**
- 4.2.2. **Listing 2: Protocol deviations according the investigator**
- 4.2.3. **Listing 3: Demographics at baseline**
- 4.2.4. **Listing 4: AF History**
- 4.2.5. **Listing 5: Medical History (1/3)**
- 4.2.6. **Listing 6: Medical History (2/3)**
- 4.2.7. **Listing 7: Medical History (3/3)**
- 4.2.8. **Listing 8: Procedure data (1/4)**
- 4.2.9. **Listing 9: Procedure data (2/4)**
- 4.2.10. **Listing 10: Procedure data (3/4)**
- 4.2.11. **Listing 11: Procedure data (4/4)**
- 4.2.12. **Listing 12: Additional Ablation**
- 4.2.13. **Listing 13: Chronic Procedural Success at remap**
- 4.2.14. **Listing 14: Primary Safety endpoints**
- 4.2.15. **Listing 15: Device Deficiencies**
- 4.2.16. **Listing 16: Adverse events according CEC review**
- 4.2.17. **Listing 17: Serious adverse events according CEC review**
- 4.2.18. **Listing 18: Concomitant Medications**

[figure not shown]
CONFIDENTIEL / CONFIDENTIAL

Toute reproduction ou distribution, totale ou partielle, de ce document, sans autorisation préalable de ICON PLC est interdite.
Reproduction and distribution of this document, in whole or in part, is strictly forbidden without prior authorization from ICON PLC.

4.3. Graphs

4.3.1. Graph 1: Patient disposition

4.3.2. Graph 2: Freedom from AF/AFL/AT on ADDs

- Summary table

	Group 1 (N=XXX)
Nb of patients	XXX
Nb of patients with an event	XX (XX.X%)
Nb of patients without an event	XX (XX.X%)
Survival rate	XX %
Time to event (days)	
Median	XX
(95% CI)	(XX, XX)
25th-75th percentile	XXX – XXX
Range	X.XX - X.XX

CONFIDENTIEL / CONFIDENTIAL

Toute reproduction ou distribution, totale ou partielle, de ce document, sans autorisation préalable de ICON PLC est interdite.
Reproduction and distribution of this document, in whole or in part, is strictly forbidden without prior authorization from ICON PLC.

	STATISTICAL ANALYSIS PLAN	FARAPULSE PersAFOne SAP V1.0 PERSAFONE Page 49 /49
---	----------------------------------	--

- 4.3.3. Graph 3: Freedom from AF/AFL/AT off ADDs**
- 4.3.4. Graph 4: Freedom from AF on AADs**
- 4.3.5. Graph 5: Freedom from AF off AADs**
- 4.3.6. Graph 6: Freedom from AF/AFL/AT, no DCCV>90 days, no RF, no ablation >90 days**
- 4.3.7. Graph 7: Freedom from AF/AFL/AT, no DCCV>90 days, no RF, no ablation >90 days on AADS**
- 4.3.8. Graph 8: Freedom from AF/AFL/AT, no DCCV>90 days, no RF, no ablation >90 days off AADS**
- 4.3.9. Graph 9: Freedom from AF, no DCCV>90 days, no RF, no ablation >90 days on AADs**
- 4.3.10. Graph 10: Freedom from AF, no DCCV>90 days, no RF, no ablation >90 days off AADs**
- 4.3.11. Graph 11: Death**

CONFIDENTIEL / CONFIDENTIAL

Toute reproduction ou distribution, totale ou partielle, de ce document, sans autorisation préalable de ICON PLC est interdite.
Reproduction and distribution of this document, in whole or in part, is strictly forbidden without prior authorization from ICON PLC.

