3.7 Sample Size

Up to 40 subjects in total will be enrolled at up to four sites in this clinical safety and feasibility study. Approved sites will enroll at least 5 and not more than 20 subjects.

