3.11.3 Blanking Period

The Blanking Period consists of Day 0 (the date of Index Procedure) through and including Day 90.

During the Blanking Period, any recurrence of AF will be documented; however, recurrences of AF, AFL or AT during this time will not be considered Therapeutic Failures.

Subjects may undergo one repeat ablation during the Blanking Period without creating a Therapeutic Failure, following the procedure detailed in the preceding sections. This may occur during the Remap Procedure or at another procedure as clinically indicated.

If a second repeat ablation procedure is performed during this time, or any nonstudy device is used for cardiac ablation, the subjects will be considered a Therapeutic Failure but will remain in the study.

Towards the end of the Blanking Period, any AFD treatment will be discontinued unless the Investigator deems the withdrawal of AFD treatment not to be in the best interests of the patient.

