6.4 Secondary Feasibility Endpoints

1. The proportion of subjects who undergo the protocol-specified 75-Day Remapping Procedure and achieve Chronic Procedural Success (CPS) defined as persistent electrical isolation of all initially ablated pulmonary veins. Chronic Procedural Success will be subdivided by Index Procedure only CPS and Reablated CPS subjects.

2. The proportion of attempted subjects that achieve Acute CTI Success, defined as the creation of bi-directional electrical block across the CTI using the investigational devices.
3. Durability of the CTI and/or other extra-PV lesion set(s), when applicable. Durability is defined as unaltered integrity of each such lesion assessed at the Remapping Procedure.
4. The proportion of subjects that achieve Therapeutic Success, defined as freedom from:
 - a. Post-Blanking Period through assessment: occurrence of AF, AFL or AT, or ablation for AF/AFL/AT using the study device
 - b. At any time: ablation for AF/AFL/AT with a nonstudy deviceTherapeutic Success will be assessed from the end of the 90 Day Blanking Period through Months 6 and 12 and will be subdivided by on / off AFDs (Atrial Fibrillation Drugs) post-Blanking Period.

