2.1.4. Inferential Analysis

- Confidence intervals:

When applicable, bilateral asymptotic or exact confidence intervals for binomial distributions will be calculated at the 95% level.

For categorical variables, if pertinent, the 95% asymptotic confidence interval will be calculated if theoretical assumptions are verified. If this is not the case, and the corresponding proportion is 0% or 100%, then the Agresti-Coull confidence interval will be calculated instead. In all other cases, the exact confidence interval will be calculated.

- Survival analysis:

Time-to-event variables will be described over time by survival curves as per the Kaplan-Meier method together with the associated estimators, considering the upper window of the corresponding visits. The survival rate will be presented at each time point (30 days, 90 days, 180 days, 365 days) and overall.

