2.2. Sample size calculation

This investigation is the next phase of ongoing feasibility studies to allow the controlled introduction of a new cardiac ablation catheter (FARAFLEX Endocardial Ablation Catheter). This is a feasibility study with no formal hypothesis testing and therefore no required sample size. Study results will be presented using descriptive statistics. Results from this study will be used to inform and design additional clinical studies.

Forty (40) subjects at up to four sites will allow the assessment of the modified devices and the initial experience and training of investigators and study staff at a new investigational site.

CONFIDENTIEL / CONFIDENTIAL

Toute reproduction ou distribution, totale ou partielle, de ce document, sans autorisation préalable de ICON PLC est interdite.
Reproduction and distribution of this document, in whole or in part, is strictly forbidden without prior authorization from ICON PLC.

	STATISTICAL ANALYSIS PLAN	FARAPULSE PersAFOne SAP V1.0 PERSAFONE Page 14 /49
---	----------------------------------	--

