2.4.6.2. Secondary Feasibility Analysis

The secondary feasibility analyses are:

- The proportion of subjects who undergo the protocol-specified 75-Day Remapping Procedure and achieve Chronic Procedural Success (CPS) defined as persistent electrical isolation of all initially ablated pulmonary veins. Chronic Procedural Success will be subdivided by Index Procedure only CPS and Reablated CPS subjects.
- The proportion of attempted subjects that achieve Acute CTI Success, defined as the creation of bi-directional electrical block across the CTI using the investigational devices.
- Durability of the CTI and/or other extra-PV lesion set(s), when applicable.
Durability is defined as unaltered integrity of each such lesion assessed at the Remapping Procedure.
- The proportion of subjects that achieve Therapeutic Success, defined as freedom from:
 - Post-Blanking Period through assessment: occurrence of AF, AFL or AT, or ablation for AF/AFL/AT using the study device
 - At any time: ablation for AF/AFL/AT with a non-study device
Therapeutic Success will be assessed from the end of the 90 Day Blanking Period through Months 6 and 12 and will be subdivided by on / off AADs (Atrial Fibrillation Drugs) post-Blanking Period.

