- Derived criteria "Durability of Left atrial roof line at remap" will be defined as follows:
IF Left atrial roof line lesion durable ='Yes' in **Follow-up 3D electroanatomical mapping form (RM)** **THEN** Durability of Left atrial roof line at remap = 'Yes'
ELSE IF Left atrial roof line lesion durable ='No' in **Follow-up 3D electroanatomical mapping form (RM)** **THEN** Durability of Left atrial roof line at remap = 'No'
- Derived criteria "Durability of Left atrial Posterior line" will be defined as follows:
IF Left atrial Posterior line lesion durable ='Yes' in **Follow-up 3D electroanatomical mapping form (RM)** **THEN** Durability of Left atrial Posterior line at remap = 'Yes'
ELSE IF Left atrial Posterior line lesion durable ='No' in **Follow-up 3D electroanatomical mapping form (RM)** **THEN** Durability of Left atrial Posterior line at remap = 'No'
- Derived criteria "Therapeutic Success ON/OFF AAD" will be defined as follows:

CONFIDENTIEL / CONFIDENTIAL

Toute reproduction ou distribution, totale ou partielle, de ce document, sans autorisation préalable de ICON PLC est interdite.
Reproduction and distribution of this document, in whole or in part, is strictly forbidden without prior authorization from ICON PLC.

IF "AF/AFL/AT status"= 0 **AND** "RF touchup"= 0 **AND** "ABL >90 days" = 0 **in MDT excel file**
THEN therapeutic success='Yes'
ELSE therapeutic success='No'

- Derived criteria "Therapeutic Success Off ADD" will be defined as follows:
IF Therapeutic success ='Yes' **AND** Class I/III AAD>90days=0 **in MDT excel file** **THEN** therapeutic success Off ADD ='YES'
ELSE IF Therapeutic success ='No' **AND** Class I/III AAD>90days=0 **in MDT excel file** **THEN** **THEN** therapeutic success Off ADD ='NO'
- Derived criteria "Therapeutic Success On ADD" will be defined as follows:
IF Therapeutic success ='Yes' **AND** Class I/III AAD>90days=1 **in MDT excel file** **THEN** therapeutic success On ADD ='No'
Else If Therapeutic success ='No' **AND** Class I/III AAD>90days=1 **in MDT excel file** **THEN** **THEN** therapeutic success On ADD ='No'

Additional endpoints

- Derived criteria "Proportion of all ablated pulmonary veins that are isolated at the Index Procedure using the study device" will be defined as follows:

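### SAP 2.5 drops failures who later start a Class I/III drug from the off-AAD Therapeutic Success denominator, so that rate would be inflated if recurrence prompts such starts

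*SAP*

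**What the plan says.** Protocol 6.4 says that Therapeutic Success "will be subdivided by on / off AFDs (Atrial Fibrillation Drugs) post-Blanking Period". SAP 2.4.6.2 repeats this: it "will be subdivided by on / off AADs (Atrial Fibrillation Drugs) post-Blanking Period". Neither gives a date for drug status or a rule for drugs started after a failure.

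Protocol 3.11.3 sets the background: "Towards the end of the Blanking Period, any AFD treatment will be discontinued", unless the investigator judges withdrawal not to be in the patient's interest. Later use is therefore either continued or newly started treatment. Recurrence is not among the withdrawal reasons in Protocol 3.10. Changes in antiarrhythmic medication are recorded at the 6- and 12-month visits (Protocol 3.12.6 and 3.12.7).

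The SAP carries out the split with one item in the MDT Excel file, listed under Databases in SAP 2.3: a Class I/III drug indicator labelled >90 days, with no start date and no minimum use. SAP 2.5 then applies it in two ways:

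- **Therapeutic Success Off AAD** is Yes for a success and No for a failure, in each case only with "Class I/III AAD>90days=0". A failure with the flag at 1 receives no off-AAD value.
- **The binary freedom variables without AAD** are Yes if the subject is arrhythmia-free and the flag is 0. Everyone else is No.

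For the curves, SAP 4.3 lists titles such as "Graph 3: Freedom from AF/AFL/AT off ADDs", SAP 2.4.5 speaks of patients on and off AADs, and SAP 2.1.4 names Kaplan-Meier. None of them defines the risk set.

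**The concern.** Group membership in the off-AAD analysis can be decided by the outcome. Take a subject off drug at day 90 who recurs on day 150 and then starts a Class I/III drug. The flag as labelled would be 1, and this off-drug failure would disappear from the off-AAD denominator of Therapeutic Success. A success has no recurrence to prompt a start. In a Kaplan-Meier curve on the flag = 0 subset, the same selection amounts to conditioning on future drug use.

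Off-drug freedom from arrhythmia is a figure a reader would carry forward, and SAP 2.2 says the results will inform the design of further studies. A rate that rises each time a failure is given a drug is a poor planning value.

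**Working it through.** **Inputs.** There is no figure in the plan to reproduce: "This is a feasibility study with no formal hypothesis testing and therefore no required sample size". The planned size comes from Protocol 3.7: "Up to 40 subjects in total will be enrolled at up to four sites". The SAP shells for Tables 5 and 19 print N = 25, used here only as a second scenario size. The documents give neither a 12-month success rate nor the share of failures who start a drug, so both are assumed below.

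**Formula.** Let S and F be the successes and failures off drug at day 90, and r the share of those failures who start a Class I/III drug after recurrence. Assume for now that no success starts one.

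- Off-AAD Therapeutic Success rule in SAP 2.5: S / (S + F(1 − r))
- Status fixed at day 90: S / (S + F)

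**Simple counts (assumed; all subjects off drug at day 90).**

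| N | Recur | Start drug after | SAP 2.5 off-AAD rule | Status at day 90 |
|---|---|---|---|---|
| 25 | 8 | 4 | 17/21 = 81.0% | 17/25 = 68.0% |
| 25 | 8 | 6 | 17/19 = 89.5% | 17/25 = 68.0% |
| 40 | 13 | 6 | 27/34 = 79.4% | 27/40 = 67.5% |

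The binary freedom rule returns 17/25, 17/25 and 27/40 in these rows, because every failure stays in as No. Two rules in one SAP section thus give 81.0% and 68.0% for the same subjects.

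**Range.** With a day-90 rate of 60%, r = 25%, 50% and 75% give 60/90 = 66.7%, 60/80 = 75.0% and 60/70 = 85.7%. With 80%, they give 84.2%, 88.9% and 94.1%.

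**Some subjects on drug at day 90 (assumed).** N = 40 with 24 successes. Four successes and two failures are on drug at day 90, and 7 of the other 14 failures start one after recurrence. SAP 2.1.4 provides that "bilateral asymptotic or exact confidence intervals for binomial distributions will be calculated at the 95% level"; exact intervals are used here.

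- SAP 2.5 off-AAD rule: 20/27 = 74.1% (53.7 to 88.9)
- Status at day 90: 20/34 = 58.8% (40.7 to 75.4)
- All ITT, free and off drug: 20/40 = 50.0%
- Unsplit: 24/40 = 60.0% under every rule
- On-AAD group under the flag: 4/(4 + 2 + 7) = 4/13 = 30.8%, against 4/6 = 66.7% by day-90 status

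As coded, though, On AAD is 0/13 = 0%, because SAP 2.5 assigns No to successes and failures alike.

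**Curves, if drawn on the flag = 0 subset.** A simulation used exponential recurrence over days 90 to 365, 60% event-free, a drug with no effect started only after recurrence, and 2,000 runs at each of N = 25 and 40. It gave day-365 estimates of about 0.66 to 0.67, 0.75 and 0.86 for r = 25%, 50% and 75%, against a true 0.60.

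**Direction.** The shift is upward only if failures carry the flag more often than successes. With 60% success overall and equal shares flagged, the off-AAD rate stays at 60%. With 40% of successes and 20% of failures flagged, it is 0.36/(0.36 + 0.32) = 52.9%.

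**The case against.** A reader might infer that every off-AAD result in the SAP is biased upward by construction. The documents do not support that, for four reasons, all of which stand:

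- The binary freedom variables count every failure as No whatever the drug status. If they feed the Off AADs rows of Table 7, as their names suggest, an uninflated figure is already planned. One version also requires no cardioversion, no RF and no ablation after day 90.
- The graphs are titles without a risk set, so the subset reading is natural but unstated.
- That the flag means any use at any time after day 90 is inferred from its label. The firm criticism is that its timing is undefined.
- The documents give no rate of drug starts after recurrence, and continued drug use among successes can push the figure down.

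The consequence is also limited. This is a secondary endpoint in a descriptive study, the unsplit rates are reported and unaffected, and medications are listed by subject.

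Fixing status at day 90 has a weakness of its own: a subject who starts a drug before any recurrence and stays arrhythmia-free would count as an off-drug success. That calls for a stated rule; it does not justify letting a drug start after failure remove the failure.

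**Conclusion.** The point holds for Therapeutic Success Off AAD. Under the SAP 2.5 rule, a failure with the flag at 1 leaves the denominator, and nothing in either document stops a drug start after recurrence from setting the flag. The off-AAD rate would then be too high if failures start drugs after recurrence more than successes use them. The size is unknown from the documents; the assumed counts put the shift at 11.9 points (79.4 − 67.5) to 21.5 points (89.5 − 68.0). The curves are affected only if drawn on the flag = 0 subset.

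The binary freedom variables and all unsplit rates are not inflated. Two further defects need no assumption: SAP 2.5 contains two incompatible off-AAD rules, and its On AAD derivation forces 0% whatever the data.

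**What to change.** 1. In SAP 2.5, compute Therapeutic Success Off AAD over all ITT subjects: Yes if free of failure and with no Class I/III drug after day 90, otherwise No. This is the form the freedom variables already use.
2. For any on/off subgroup rate or curve, define the flag with a date, classify by drug status at the end of the Blanking Period, and ignore drug starts after the first failure. State the risk set for Graphs 2 to 5 and 7 to 10.
3. State how the day-90 split treats a subject who starts a drug before any recurrence.
4. Correct the On AAD derivation so that a success with the flag at 1 is Yes.

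**Cost.** Items 1 and 4 are wording and a few lines of code. Items 2 and 3 need medication start dates from the CRF, since the MDT file lists a flag without a date. There is no day-90 visit (the nearest are at 75 ± 15 and 180 ± 30 days), so status at day 90 must be derived from those dates, and it should be confirmed that they are captured. The off-AAD figure may be less favourable. The all-ITT figure also answers a different question, since arrhythmia-free drug users count against it, so it should be labelled as free of failure and off drug.
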